### **2.5.2.6 Mechanism of action**

Metformin is an antihyperglycemic agent which improves glucose tolerance in patients with type 2 diabetes, lowering both basal and postprandial plasma glucose. Metformin decreases hepatic glucose production, decreases intestinal absorption of glucose, and improves insulin sensitivity by increasing peripheral glucose uptake and utilization. It does not cause hypoglycaemia and hyperinsulinaemia.

As discussed above, the proposed mechanisms for the treatment of pre-eclampsia are the following:

- Metformin inhibits hypoxic inducible factor 1 $\alpha$  (HIF 1 $\alpha$ )
- Metformin reduces sFlt-1 and sENG secretion from primary endothelial cells and placental tissue
- Metformin reduces VCAM-1 expression on endothelial cells
- Metformin induces vasodilation in maternal vessels and enhances angiogenic sprouting.

### **2.5.2.7 Pharmacokinetics**

The absolute bioavailability of metformin 500mg tablet given under fasting conditions is approximately 50% to 60%. Studies using single oral doses of metformin 500mg to 1500mg, and 850 to 2550mg, indicate that there is a lack of dose proportionality with increasing doses, which is due to decreased absorption rather than an alteration in elimination.

Food decreases the extent of, and slightly delays the absorption of metformin, as shown by approximately a 40% lower mean peak plasma concentration (Cmax), a 25% lower area under the plasma concentration versus time curve (AUC), and a 35-minute prolongation of time to peak plasma concentration (Tmax) following administration of a single 850mg tablet of metformin. Cmax is achieved with a median value of 7 hours and a range of 4 to 8 hours.

After repeated administration metformin did not accumulate in plasma.

Metformin is negligibly bound to plasma proteins. Metformin partitions into erythrocytes, most likely as a function of time. At usual clinical doses and dosing steady state plasma concentrations of metformin are reached within 24 to 48 hours and are usually <1  $\mu$ g/mL. During controlled clinical trials, maximum plasma levels did not exceed 5  $\mu$ g/mL, even at maximum doses.

Metformin is excreted unchanged in the urine and does not undergo hepatic metabolism or biliary excretion. Renal clearance is approximately 3.5 times greater than creatinine clearance, which indicates that tubular secretion is the major route of metformin elimination. Following oral administration, approximately 90% of the absorbed drug is eliminated via the renal route within the first 24 hours, with a plasma elimination half-life of approximately 6.2 hours. In blood, the

elimination half-life is approximately 17.6 hours, suggesting that the erythrocyte mass may be a compartment of distribution.

## **2.6 Summary**

Currently, the only option for the treatment of pre-eclampsia is delivery. At extremely premature gestations this subjects the neonate to the risk of significant morbidity and mortality.

Preclinical and clinical data has uncovered potent biological actions suggesting metformin may be a lead candidate therapeutic to treat pre-eclampsia. Treatment with metformin in pregnancy is considered safe as it is used extensively for the treatment of diabetes.

We have a unique collaboration between Stellenbosch and Melbourne University that allows us to test this hypothesis in Tygerberg Academic Hospital, South Africa. This population has a high prevalence of early onset pre-eclampsia. We have completed the Pre-eclampsia Intervention trial with Esomeprazole (PIE) and his trial shows that the collaboration is successful, efficient and cost effective..

## Aims and Objectives

### 3.1 Specific Aims and Outcomes:

#### Primary aim:

- 1) To examine whether metformin can prolong gestation in women with early onset pre-eclampsia diagnosed 26+0 – 31+6 weeks who are being managed expectantly as compared to expectant management alone.

#### Primary outcome:

- 1) Prolongation of gestation measured from the time of enrolment to the time of delivery, in hours and days.

#### Secondary aims:

- 2) To determine whether metformin can improve 1) maternal 2) fetal and 3) neonatal outcomes in early onset pre-eclampsia being managed expectantly compared to expectant management alone.
- 3) To examine whether metformin can significantly decrease levels of circulating sFlt-1 and/or sEng in women with early onset pre-eclampsia who are being managed expectantly compared to expectant management alone.
- 4) To examine whether metformin is safe and well tolerated in the mother and infant, compared with placebo.

### 3.2 Hypothesis

#### Primary Hypothesis:

- 1) Metformin can prolong gestation in women with early onset pre-eclampsia, compared to expectant management alone.

**Other hypotheses:**

- 2) Metformin improves maternal, fetal and neonatal outcomes, in women diagnosed with early onset preeclampsia, compared to expectant management alone.
- 3) Metformin decreases the circulating levels of sFlt1 and sEng in early onset preeclampsia being managed expectantly compared to expectant management alone.

## Study Design

### 4.1 Type of study

Hospital based phase II placebo-controlled, double-blind parallel randomised control trial.

To classify the phase of this study is somewhat difficult given metformin is already an approved drug. Historically pregnant women and children have been excluded from all phase 1 trials as they do not fall under the category of “healthy volunteers”. This makes any trial in pregnant women more difficult. Furthermore, phase I trials are typically those where the primary outcome is safety.

We have classified this trial as a phase 2 trial as we will be assessing efficacy. We aim to determine whether metformin is effective for the treatment of pre-eclampsia.

### 4.2 Study population

Tygerberg Hospital has extensive experience with the management of early onset pre-eclampsia (37). Pregnant women diagnosed with early onset pre-eclampsia at a gestational age between 26+0 weeks to 31+6 weeks who qualify for expectant management. Women who consent and meet eligibility criteria (see 5.2) will be enrolled in the study.

### 4.3 Intervention

Participants will be randomised to administration of either active tablets containing metformin or an identical placebo. Once they have been recruited they will start by taking one tablet twice a day. If they have no side effects after 24 to 48 hours they will increase to 2 tablets twice a day. If again they experience no side effects after 24 to 48 hours they will increase to 3 tablets twice a day. If they are not tolerating the tablets the dose can also be decreased. The maximum dose of metformin will be 1.5mg in the morning and evening. Treatment will continue until delivery. The study will not alter or interfere with any treatment or care given routinely to women with early onset pre-eclampsia.

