## **1.4 Aims**

### **1.4.1 Primary aim**

To examine whether 3 grams of metformin daily can safely further prolong gestation for 5 days in women with early onset pre-eclampsia diagnosed 26+0 – 31+6 weeks, compared to standard of care, expectant management alone.

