#### **7.2.5 Dosage**

Metformin use is associated with side effects that include nausea and diarrhoea. We will start all participants on six tablets a day in divided doses. If a participant does experience side effects, we will decrease until the side effects improve. We may then increase the medication back up to 6 tablets a day if the side effects improve and the patient is willing to increase the medication again.

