17. Description of any planned adjustment for multiplicity, and if so, including how the type 1 error is to be controlled

No adjustment for multiplicity will be performed. The strategy for outcome testing is pre-specified and maintains the overall trial error rate at 0.05.

18. Confidence intervals (CI) to be reported

Standard 95% confidence intervals will be used to present analysis of the primary adjusted outcome. For secondary outcomes it is planned to the adjusted width of CI used.³

19. Adherence and Protocol Deviations

Adherence:

Trial medication will be administered to mothers on an inpatient basis. Measures to monitor adherence are: The trial medication will be written up on the treatment chart and the chart will be signed by the nursing staff to confirm that the participant has taken the medication and to confirm compliance. The research midwife will monitor the treatment chart to assure compliance. The dosing schedule details a programmed escalation of dose in the of side effects. We will use two measures of dosing in the metformin arm: (i) average daily dose of tablets = number of ingested medications/days of therapy and (ii) percentage of maximum dose = ingested medications/ total maximum medications.

Description of how adherence to the intervention will be presented:

Adherence will be presented on the two measures detailed above, using descriptive statistics (N, mean, SD, median, minimum, maximum) converted to metformin dose for the intervention arm.

Definition of protocol deviation for the trial and description in trial results:

Protocol deviations due to errors in applying inclusion/exclusion criteria, the wrong intervention being administered will be documented in trial results either in patient flow diagram or text. The primary outcome will not be subject to ascertainment error due to its unambiguous nature. Prior to unblinding of treatment all protocol deviations will be assessed, and determination made about inclusion of these participants within the trial analysis populations. Determinations will be presented in the research results in the patient flow diagram and possibly in the text.

³ Ludbrook J. Multiple inferences using confidence intervals. Clin Exp Pharmacol Physiol 2000;27:212 - 215.

19. Analysis populations.

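### Protocol 4.3 and 7.2.5 give starting regimens that cannot both be followed, and the maximum dose in 4.3 does not agree in units with the dose in the aims

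*Protocol*

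**What the plan says.** Protocol 4.3 (Intervention) describes upward titration. After recruitment, "they will start by taking one tablet twice a day". The next step is "If they have no side effects after 24 to 48 hours they will increase to 2 tablets twice a day", and after a further 24 to 48 hours without side effects "they will increase to 3 tablets twice a day". The dose may also be lowered if it is not tolerated. The same section gives a ceiling: "The maximum dose of metformin will be 1.5mg in the morning and evening".

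Protocol 7.2.5 (Dosage) describes downward titration. "We will start all participants on six tablets a day in divided doses", and then "If a participant does experience side effects, we will decrease until the side effects improve", with a possible return to six a day.

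The protocol's primary aim (1.4.1) is "To examine whether 3 grams of metformin daily can safely further prolong gestation for 5 days". SAP 8 gives 3 grams as the daily dose in its research hypothesis and as an upper limit in its primary objective.

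The SAP section on adherence says "The dosing schedule details a programmed escalation of dose", but that sentence continues with words missing. The section defines two exposure measures, average daily tablets and percentage of maximum dose, and reports them converted to metformin dose. SAP 24 defines treatment received, for the first sensitivity analysis of the primary outcome, as an average daily dose.

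**The concern.** A site cannot apply both dosing sections to the same woman. They differ in starting tablet count and in the direction of titration. Under Protocol 7.2.3 the medication is written up on a treatment chart that nurses sign, so the chart has to reflect one section or the other. Staff working from different sections would give different early exposure.

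Three sets of results would then depend on which section was followed:

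- **Tolerability.** Draft Table 4 of the SAP counts women whose tablets were decreased. Under 4.3, a woman with side effects on two tablets a day may simply not be stepped up, and so would not be counted. Under 7.2.5, a woman with side effects on six a day is reduced and counted.
- **Dose summaries.** Average daily dose and percentage of maximum dose carry a built-in shortfall under 4.3 that is absent under 7.2.5.
- **Treatment-received analysis.** Under 4.3 the average daily dose rises with time on treatment, and time on treatment closely tracks the primary outcome. Under 7.2.5, with full tolerance, it does not.

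Separately, the ceiling in 4.3 is in milligrams and the dose in the aims is in grams. Without a stated tablet strength, the tablet counts cannot confirm the intended daily amount.

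**Working it through.** **Stated maximum.** From 4.3: 2 × 1.5 mg = 3 mg a day. From Protocol 1.4.1 and SAP 8: 3 g = 3000 mg a day. The ratio is 3000 / 3 = 1000, so the two figures do not agree.

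**Implied tablet content.** Three tablets twice a day is six a day, the top step in 4.3 and the starting count in 7.2.5.

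- From the 4.3 ceiling: 1.5 mg / 3 tablets = 0.5 mg per tablet.
- From 3 g a day: 3000 mg / 6 tablets = 500 mg per tablet.

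Protocol 2.5.2.1 lists marketed strengths of 500, 850 and 1000 mg, and 500 or 750 mg for extended release. Six tablets of these would give 3000, 5100, 6000 or 4500 mg respectively (500, 850, 1000 and 750 mg). No listed strength is near 0.5 mg, which is why this looks like a unit discrepancy. The list covers marketed products, however, and neither document gives the strength of the trial tablet.

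**Tablets in the first four days**, assuming full tolerance and full adherence:

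- 4.3 with 24-hour steps: 2 + 4 + 6 + 6 = 18
- 4.3 with 48-hour steps: 2 + 2 + 4 + 4 = 12
- 7.2.5: 4 × 6 = 24

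**Tablets over D days** (D at least twice the step length). With steps of s days, 4.3 gives 2s + 4s + 6(D − 2s) = 6D − 6s, and 7.2.5 gives 6D. The shortfall is fixed at 6 tablets (s = 1) or 12 tablets (s = 2). The control median of 8.32 days is from the footnote to Table 1 in Protocol 4.4.

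| Days to delivery | 7.2.5 total | 4.3, 24 h steps | 4.3, 48 h steps |
|---|---|---|---|
| 5 | 30 | 24 (80%) | 18 (60%) |
| 8.32 | 49.9 | 43.9 (88%) | 37.9 (76%) |
| 21 | 126 | 120 (95%) | 114 (90%) |

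At 8.32 days the average under 4.3 is 43.9 / 8.32 = 5.28 or 37.9 / 8.32 = 4.56 tablets a day, against 6 under 7.2.5.

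**Effect on the percentage measure.** Take a woman who follows 4.3 perfectly and delivers at 8.32 days. If the denominator is six tablets on every day, she scores 76% to 88%. If it is the maximum scheduled for each day, she scores 100%. The SAP does not say which is meant.

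**Link between average dose and outcome.** Under 4.3 with 48-hour steps, delivery at day 2 gives 4 / 2 = 2 tablets a day and delivery at day 21 gives 114 / 21 = 5.4. With 24-hour steps the values are 6 / 2 = 3 and 120 / 21 = 5.7. Under 7.2.5 both are 6.

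**The case against.** The strongest defence is that the sections agree on more than they dispute. Both use tolerance-guided dosing up to six tablets a day, treatment runs to delivery, and only the first few days differ. Over longer treatment the gap shrinks to 5% to 10% at 21 days. The primary analysis is by randomised group, and the sample size rests on prolongation and its variability, so neither depends on the starting step. This stands, and it limits the reach of the point. It does not remove the conflict: 7.2.5 applies to all participants at the start, so it cannot be read as a later phase of 4.3.

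Four stronger readings might be inferred, and the documents do not support them:

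- **A thousand-fold dosing error.** Tablets are given by count from identical pre-packed supplies (Protocol 7.2.1 and 7.2.3), and both sections share the six-tablet ceiling. No route to such an error is described.
- **Damage to blinding.** Both arms follow the same tablet schedule with an identical placebo. Side effects could hint at allocation under either regimen, and nothing shows that the conflict makes this worse.
- **The SAP endorses 4.3.** Its mention of escalation leans that way, but the sentence is incomplete, and 7.2.5 also allows an increase back to six.
- **The percentage measure has no usable denominator.** If the SAP's total maximum medications means six a day throughout, the denominator is the same under both sections. It is ambiguous only because the scheduled daily maximum is also a possible meaning.

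**Conclusion.** The point holds as an internal contradiction that must be reconciled. The starting count differs threefold (2 against 6 tablets a day), with titration in opposite directions. The consequence is 12 to 18 against 24 tablets in the first four days, and 76% to 88% of the six-a-day total over 8.32 days. These figures assume full tolerance and adherence, and steps taken at exactly 24 or 48 hours. Using the 48-hour, four-day figure alone would overstate the difference.

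The milligram and gram figures disagree as printed. A unit discrepancy is the likely explanation, but it is an inference because the tablet strength is not stated.

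What is affected is early exposure, side-effect and dose-reduction counts, the SAP dose summaries and the treatment-received sensitivity analysis. The intention-to-treat analysis method and the sample size are unaffected. The correction matters because the protocol governs how the treatment chart is written. Which regimen or dose is right is for the responsible clinicians and is not judged here.

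**What to change.** 1. The responsible clinicians reconcile Protocol 1.4.1, 4.3 and 7.2.5 with SAP 8 and the SAP adherence section, so that all give one starting regimen, one titration rule and one maximum in consistent units.
2. State the strength of the trial tablet, so that tablet counts convert to metformin dose as the SAP intends.
3. Check the treatment-chart templates against the reconciled text.
4. In the SAP, complete the broken sentence on escalation. State whether total maximum medications means the ceiling dose on every day or the maximum scheduled for each day.

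The cost is protocol amendment wording, a short SAP revision and a check of the chart templates. Nothing changes in the sample size or the primary analysis.

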### **2.5.2.2 Contraindications**

Metformin is contraindicated in

- Renal disease or renal dysfunction (suggested by serum creatinine levels  $\geq 123\mu\text{mol/L}$  or abnormal creatinine clearance) which may also result from conditions such as cardiovascular collapse (shock), acute myocardial infarction, and septicemia.

- Known hypersensitivity to metformin hydrochloride.
- Acute or chronic metabolic acidosis, including diabetic ketoacidosis, with or without coma.

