### **2.5.2.3 Warnings and precautions**

There is very small risk of lactic acidosis (0.03 cases/1000 patient years) and reported cases have been associated with renal insufficiency which is a contraindication for the use of metformin. Patients should be warned of the following nonspecific symptoms which include malaise, myalgia, respiratory distress, somnolence and nonspecific abdominal pain and should report these symptoms to their attending physician.

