## 5.3 Exclusion criteria

- Patient is unable or unwilling to give consent
- Established fetal compromise that necessitates delivery. This will be decided by the clinical team before expectant management is offered to the patient.

- Suspicions of a major fetal anomaly or malformation. A major fetal anomaly is defined as anomalies or malformations that create significant medical problems for the patient or that require specific surgical or medical management. Major anomalies or malformations are not considered a variation of the normal spectrum.
- The presence of any of the following at presentation:
  - Eclampsia defined as the new onset of grand mal seizure activity and/or an unexplained coma during pregnancy with signs or symptoms of pre-eclampsia.
  - Severe hypertension defined as a systolic blood pressure greater than or equal to 160 mmHg or diastolic blood pressure greater than or equal to 110 mmHg that cannot be controlled with antihypertensive medication within 48 hours of admission.
  - Cerebrovascular event defined as an ischaemic or haemorrhagic stroke associated with clinical symptoms and definitive signs on imaging.
  - Posterior reversible encephalopathy syndrome (PRES) associated with pre-eclampsia defined on imaging as reversible vasogenic oedema, usually in the occipital or parietal lobes.
  - Severe renal impairment with a creatinine level of greater or equal to 125 µmol/l or a need for dialysis.
  - Signs of left ventricular failure which include pulmonary oedema requiring treatment or oxygen saturations of less than 90% caused by left sided heart failure.
  - Disseminated intravascular coagulation defined as an INR greater than 2
  - Platelet count at presentation less than  $50 \times 10^9$  (platelet aggregation excluded)
  - Haemolysis, elevated liver enzymes and low platelets (HELLP) syndrome defined as a platelet count less than  $100 \times 10^9/L$ , aspartate aminotransferase greater than 60 µ/L, and haemolysis as demonstrated by lactate dehydrogenase > 600 µ/L or haemolysis on a peripheral blood smear.
  - Liver transaminases greater than or equal to 500IU/L
  - Liver haematoma or rupture
  - Fetal distress on cardiotocography
  - Severe ascites on ultrasound as defined by the sonographer
- Contra-indications for expectant management of pre-eclampsia
- Current use of metformin or a clinical indication for the use of metformin
- Contraindications to the use of metformin

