### **7.2.3 Route of administration, dosage regimen and treatment period**

Each participant will be given a treatment pack by the study nurse. A copy of the randomisation number (from the randomisation website) will be placed in the participants trial folder. The treatment pack will be labelled with the participants name and trial number. The treatment pack will contain treatment for 21 days. Treatment will then be taken twice daily until the pregnancy has ended. Trial drugs will be kept in the packaging they are provided in and will under no circumstances be used for other participants. The trial medication will be written up on the treatment chart and the chart will be signed by the nursing staff to confirm that the participant

has taken the medication and to confirm compliance. The research midwife will monitor the treatment chart to assure compliance. As a second compliance check the patient will be asked to return the empty packaging to the research midwife who will record the number of empty tablet containers at the time of delivery of the patient.

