## **7.6 Withdrawal from the study**

All participants will be informed that they are free to withdraw from the study at any time, and that this will not affect their clinical care. In the event of a withdrawal, we will ask whether we can still collect further clinical data and include them in our analyses. Basic clinical data and samples already collected will be included in the analysis in accord with the consent obtained at trial entry.

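### No section of the protocol or SAP says what to do with the study tablets when an on-study creatinine reaches the level the protocol calls a contraindication to metformin

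*Protocol*

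**What the plan says.** **Duration.** Protocol section 4.3 states "Treatment will continue until delivery", and section 7.2.3 repeats it: "Treatment will then be taken twice daily until the pregnancy has ended". The full dose is 3 g a day (section 1.4.1; SAP section 8), given as six tablets.

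**Dose changes.** Section 4.3 lets the dose go up if there are no side effects and down if the tablets are not tolerated. Section 7.2.5 says: "If a participant does experience side effects, we will decrease until the side effects improve". It then allows a return to six tablets a day if the side effects improve and the woman agrees.

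**Leaving treatment.** Section 7.6 describes withdrawal as the participant's choice: "All participants will be informed that they are free to withdraw from the study at any time". Protocol sections 9.5 and 11.2 and SAP section 13 deal with stopping the trial, not with stopping one woman's tablets.

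**Kidney function and metformin.** Section 2.5.2.7 says "approximately 90% of the absorbed drug is eliminated via the renal route within the first 24 hours". Section 2.5.2.2 lists as a contraindication "Renal disease or renal dysfunction (suggested by serum creatinine levels" of 123 µmol/L or more, or an abnormal creatinine clearance). Section 2.5.2.3 says of lactic acidosis that "reported cases have been associated with renal insufficiency which is a contraindication for the use of metformin". Section 5.3 excludes, at presentation, "Severe renal impairment with a creatinine level of greater or equal to 125" µmol/L or a need for dialysis. The same section separately lists a creatinine above 124 as a contraindication to metformin.

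**Monitoring.** Creatinine is measured twice weekly as routine care (sections 7.3.1 and 7.5.1).

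**The concern.** A creatinine of 125 µmol/L bars a woman from starting metformin. The same value a week into treatment is recorded as an exploratory outcome (section 6.3.1), and nothing is said about the tablets.

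The protocol expects renal decline in this population. Severe renal impairment is part of the maternal composite (section 6.2.1), and renal failure is an expected serious event (section 9.3). The reason given for the contraindication applies to continuing the drug as much as to starting it, because the drug is cleared by the kidney and reported lactic acidosis is tied to renal insufficiency.

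If the duration and dosing rules are followed literally, a woman could stay on up to 3 g a day at a level the protocol calls contraindicated, under a clinician who does not know her arm (section 1.5). What is at stake is safety and consistent handling. The primary estimate is not at stake.

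**Working it through.** The plan has no figure to reproduce here. The check is a search for a rule, followed by simple arithmetic on exposure.

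**Step 1: every place where a creatinine level or renal event appears, and the action attached to it.**

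| Place | Level or event | Stated action |
|---|---|---|
| Protocol 2.5.2.2 | 123 µmol/L or more | Contraindication to metformin; no on-study instruction |
| Protocol 5.3, at presentation | 125 or more, or dialysis | Not enrolled |
| Protocol 5.3, metformin contraindications | Above 124 | Not enrolled |
| Protocol 6.2.1 | Severe renal impairment or dialysis | Counted in the maternal composite |
| Protocol 6.3.1 | 125 or more | Counted as an exploratory outcome |
| Protocol Table 3 | Above 150, no prior renal disease | Listed as a complication that warrants delivery |
| Protocol 9.3 | Renal failure | Reported as an expected serious event |
| SAP Table 4 | Stopped medication (any reason) | Counted; no criterion given |

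The only on-study creatinine level tied to a clinical action is above 150, and that action is delivery. No row holds, reduces or stops the tablets.

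**Step 2: the entry limits do not quite agree.** For whole-number results, above 124 and at least 125 are the same rule. At least 123 is not. Values of 123 and 124 are therefore contraindicated in section 2.5.2.2 but eligible in section 5.3. The difference is small, but a hold rule needs one number.

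**Step 3: drug taken between two results.**
- Tablet strength: 3 g / 6 tablets = 500 mg.
- Twice-weekly testing leaves gaps of 3 or 4 days.
- Full dose: 3 × 3 g = 9 g (18 tablets) to 4 × 3 g = 12 g (24 tablets).
- First dose step in section 4.3 (two tablets, 1 g a day): 3 g (6 tablets) to 4 g (8 tablets).

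These are amounts taken only if nobody acts on the result. Section 7.2.5 starts women on six tablets a day, so under that section the full-dose figure can apply from the start.

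**Step 4: how often a rule could act.** Over the control median of 8.3 days (section 4.4), 8.3/4 = 2.1 to 8.3/3 = 2.8, so about two scheduled results per woman.

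**Step 5: number of women.** The documents give no rate of on-study creatinine at this level, so the number cannot be derived. Purely as an assumption, let a proportion p of the 75 metformin women reach it. The expected number is 75p, and the chance of at least one is 1 − (1 − p)^75.

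| Assumed p | 75p | Chance of at least one |
|---|---|---|
| 0.5% | 0.375 | 31% |
| 1% | 0.75 | 53% |
| 2% | 1.5 | 78% |
| 5% | 3.75 | 98% |

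The table shows only how the answer moves with p. It concerns a creatinine reading, not harm.

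**The case against.** The case for leaving the text alone has real force.

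- **A level is already stated.** Sections 2.5.2.2 and 2.5.2.3 speak of a contraindication to the use of metformin, not only to starting it. A clinician reading them has a number. This stands: what is missing is the instruction that applies it to women already on treatment.
- **The women are watched closely.** They are inpatients assessed twice daily (section 7.3.1), at a single centre. Serious events go to the principal investigator as soon as they are identified (section 9.3), the research midwife monitors the treatment chart (section 7.2.3), and SAP section 13 relies on direct observation. This stands and narrows the gap considerably.
- **Delivery ends treatment.** Section 5.3 calls 125 or more severe renal impairment, and section 7.3.1 allows delivery for major maternal complications, so delivery is possible well below 150. This stands in part. It is a discretionary obstetric decision in a trial that aims to prolong pregnancy, and it gives no instruction about the tablets.
- **The stated risk is tiny.** Taking 75 women × 13.1 days (the placebo mean from the previous trial, section 4.4) / 365.25 = 2.7 patient-years. At 0.03 per 1000 patient-years (section 2.5.2.3), about 0.00008 cases of lactic acidosis are expected; a rate 100 times higher gives 0.008. The rate is general and not specific to renal impairment, so it neither measures the risk here nor supports alarm.
- **A rule may exist elsewhere.** The monitoring committee charter (SAP section 13), trial manuals (Protocol section 11.3), linked product information (section 2.5.2) and hospital protocols were not available. This stands.

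A reader might infer that the protocol forbids stopping the drug. It does not: until delivery is the planned duration, clinical care is discretionary, unblinding is available (section 9.4), and SAP Table 4 expects some women to stop.

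**Conclusion.** The point holds as a gap in written instructions. In the documents supplied, study drug runs until delivery, dose changes depend only on side effects or tolerability, and nothing says what happens to the tablets when a twice-weekly creatinine reaches the protocol's own contraindication level of about 123 to 125 µmol/L. It should be fixed because it concerns pregnant women on a renally cleared drug and the fix is cheap.

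The practical risk is probably small, given inpatient observation and the freedom to stop the drug or deliver. Three stronger readings are not supported:

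- That a known number of women would be exposed or harmed. The documents give no rate, and the percentages above rest entirely on assumed values.
- That no rule exists anywhere. The charter and manuals were not available.
- That the primary result is compromised. Analysis is by intention to treat, and nothing here biases it.

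The conclusion assumes that no unsupplied document already contains the rule. Confidence is medium for that reason.

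**What to change.** 1. Amend Protocol sections 4.3, 7.2.3 and 7.2.5: when an on-study creatinine reaches the stated limit, study drug is held, in either arm and without unblinding. The test is repeated. Treatment restarts only if the value falls below the limit; otherwise it stops permanently. No dose increase is allowed at or above the limit.
2. State one limit in section 2.5.2.2 and in both places in section 5.3. At least 123 µmol/L is the cautious choice; the rule also works at 125.
3. Continue follow-up and intention-to-treat analysis after any hold or stop. Record renal holds and stops as a separate reason under the stopped-medication row of SAP Table 4. Held days also lower the average daily dose used in the treatment-received sensitivity analysis (SAP section 24), so the reason needs to be visible.
4. If the charter or a trial manual already contains such a rule, cite it in sections 4.3 and 7.2.5 instead.

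The cost is a few sentences of amendment and one line in a table. The scheduled creatinine is already measured; the only possible extra is a repeat after a hold, which could be the next routine sample. The downside is slightly less drug exposure in a few women. A hold with a repeat test is preferable to a permanent stop on one reading, because a single value may not persist.
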